#### *Healthy Start to Feeding (HSF) Intervention*

The HSF intervention provides parent education and skills training on a responsive feeding approach to introduction of healthy foods in infancy through 3 sessions when the child is 4, 6, and 9 months. Each session content is manualized and administered by interventionists with expertise in child development and behavioral strategies for managing child eating behaviors under the supervision of a licensed clinical child psychologist and pediatric occupational therapist with expertise in infant eating behavior and oral motor skills. Sessions are conducted individually with each infant participant and at least one of their primary caregivers at PI [name]'s research lab and include educational content, handouts and instructions, modeling of skills by the interventionist, caregiver practicing of skills in session, establishment of behavioral goals, and problem solving barriers to implementation of treatment content. Content will include: delaying introduction of solid foods until 6 months of age, allowing infants' own hunger and satiety cues to guide the feeding experience, introducing healthy foods (e.g., fruits, vegetables, not junk food), parental attunement to infant satiety cues, reducing choking risk, and promoting infants' own self-feeding.

All intervention sessions will be audio recorded using a portable handheld digital audio recorder for use specifically for this study. Audio recordings are being obtained in order to assess treatment fidelity and whether interventionists cover the manualized content at each session. After the sessions are recorded, they will be transferred from the audio recording device to the secure UC storage network. One-third of sessions will be coded for treatment fidelity independently by two research assistants who did not provide intervention sessions. Reliability of coding will be calculated by comparing coding of the two research assistants.

If a participant withdraws participation from the study or can no longer be reached/Contacted

about study participation, all data already collected for that participant will continue to be used for the study. The alternative to participating is to not participate.

Participants may potentially be asked to participate in future studies examining the long-term outcomes of participation in our intervention. Conducting this future study, and subsequently the invitation of participants to enroll in this future study, is currently uncertain and will be determined in the future based on results of the current study and subsequent funding.

Participants will be made aware of the possibility of being asked to participate in future research during the consent process. They can decline to be approached about future research by notifying the research staff member of this desire at their last study visit. Participant interest in being contacted for future research does not impact their ability to participate in the current study.

**(c) Data collection tools**

Infant Anthropometrics. Anthropometrics will be measured for pre-post analyses at both the initial and final study visit by Bionutrition Core staff at the SRC. Infant length will be measured in triplicate to the nearest 0.1 centimeter using an infant length board (O'Leary, Ellard Instrumentation, LTD). Weight will be measured in triplicate to the nearest 100 grams with the infant in a dry diaper using a Scale Tronix 4802 digital infant/pediatric scale. The average of the three measurements will be used to calculate weight for recumbent length. Percentiles for each infant's weight for recumbent length will be obtained using sex and age specific World Health Organization (WHO) growth charts. Information will be recorded on the "Anthropometrics Form".

For families in the intervention condition, infants will also have length and weight measured at each treatment session to monitor safety of growth. Measurements will be taken by study interventionists using a SECA infant length board (SECA 416) and SECA infant digital scale (SECA 374).

Infant and Family Demographics. Demographics information will be collected at the initial study visit using a form created for use in this study.

Treatment Satisfaction. Caregivers in the treatment condition will complete a survey to provide quantitative and qualitative feedback on the intervention after the final treatment session. The questionnaire includes Likert scale ratings of the appropriateness, helpfulness, and timeliness of session content as well as open-ended questions for the parent to provide qualitative feedback on ways to improve the intervention (e.g., additional content to cover).

Infant Appetite. Parents will complete a survey entitled the *Baby Eating Behaviour Questionnaire* (Llewellyn et al., 2010) at both the initial study visit and final study visit or final treatment visit to assess current infant appetite. Parents respond to 17 items on a 5-point scale. Scores for "Enjoyment of Food", "Food Responsiveness", "Slowness in Eating", and "Satiety Responsiveness" are calculated.

Block Food Frequency Questionnaire. Parents will complete the Block Food Frequency Questionnaire for Children Aged 0-2 at the initial and post-treatment study visits. This questionnaire asks reporters to identify how frequently their child has eaten a list of foods in the last week and data are analyzed by a commercial company NutritionQuest to produce scores for daily calorie, fat, and nutrient values. Additionally for the current study, we will also calculate the number of unique foods consumed by infants during the last week

as a measure of diet variety. Participants will complete a paper booklet answer questions at the study visits, and these books are sent without any identifying information to NutritionQuest for processing.

Infant Feeding Questionnaire (IFQ; Baughcum et al., 2001). Parents will complete the IFQ, which assesses maternal feeding practices and beliefs, at the initial and post-treatment study visits. The version used in the current study is adapted to assess current feeding practices and beliefs and has been used in prior research (McMeekin et al., 2013; [name] et al., under review). The measure includes 20 items that assess parental beliefs: "Concern about Infant Undereating and Becoming Underweight", "Concern About Infant Hunger", "Concern about Infant Overeating and Becoming Overweight" and parental feeding practices: "Awareness of Infant's Hunger and Satiety Cues", "Feeding Infant on a Schedule", "Using Food to Calm Infant's Fussiness", and "Social Interaction with the Infant During Feeding". Parents respond to use question on a 5-point Likert scale or indicate n/a if appropriate.

List:

Anthropometrics Form  
Demographics Form  
Treatment Satisfaction Survey  
Baby Eating Behavior Questionnaire  
Block Food Frequency Questionnaire  
Infant Feeding Questionnaire  
Choking Incident Form

(d) Payments to participants: reimbursement of expenses or payment for time and effort

Participants will receive \$100 for participating. All study participants will receive \$50 in gift cards for completion of the first study visit and \$50 in gift cards for completion of the final study visit. Participants will also have the cost of parking for attending visits covered.

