### d. FACILITIES

Baseline and post-treatment study visits to collect outcomes measures will occur at the Schubert Research Clinic (SRC) located in the T-building at Cincinnati Children's Hospital

Medical Center (CCHMC). Intervention sessions will occur at the PI's research lab (the Healthy Kids Lab) located in the Edwards Center on UC Main Campus. We have been approved for access to these facilities.

e. DURATION OF STUDY

The research project will take 12 months to complete.

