Study participants will be assigned to either the control or treatment condition at their first study visit following completion of informed consent and baseline measures. A computer-generated random number list will be used to determine condition assignment for each participant. Participants will be notified immediately at the study visit of their study condition.

(b) Activities and duration

The first study appointment will occur when the infant is 3 months of age (defined as 3 months 0 days – 3 months 30 days) at the Schubert Research Clinic (SRC) at CCHMC. The infant and at least one parent will attend the appointment. The appointment will begin with completion of the informed consent process with the study PI or trained research assistant. Next, participants will

complete study measures, including infant anthropometrics and parent-report measures of demographics, parental feeding practices and beliefs, and infant appetite. Families will also receive information about how to intervene if their child experiences a choking incident while introducing complementary foods. Following completion of study measures, families will be randomized to either the control or treatment condition using a computer-generated random number list. Participants will receive \$50 for completion of this visit. Participants in the intervention condition will be instructed to not introduce their child to complementary foods prior to their first Treatment Session at 4 months of age. All families will receive safety information regarding monitoring infant growth and choking.

Participants assigned to the treatment condition will attend 3 intervention sessions at the Healthy Kids Lab, located in the Edwards Center on UC campus. The sessions will be scheduled with individual families when the child is 4 months (+/- 30 days), 6 months (+/- 30 days), and 9 months (+/- 30 days) of age. An attendance log of whether participants attend treatment will be kept.

All participants will also complete a final study visit at the SRC at CCHMC when the child is 9 months (+/- 30 days) of age. They will complete a final study visit to complete post-treatment period measurements, which will include infant anthropometrics and parent-report of infant appetite, infant diet, and parental feeding practices and beliefs. Families receiving the intervention will also complete a measure of treatment satisfaction. Participants will receive \$50 for completion of this visit.

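### The post-treatment BEBQ may be completed at a visit that only the treatment arm has, contrary to the rest of the Protocol

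*Protocol*

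**What the plan says.** Protocol 3.c.3(c), under Infant Appetite, has the BEBQ completed "at both the initial study visit and final study visit or final treatment visit to assess current infant appetite". It gives no rule for which of the two closing occasions applies.

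Protocol 3.c.3(b) is more definite. On the closing assessment it says "All participants will also complete a final study visit at the SRC at CCHMC", and it describes the measurements taken there as ones "which will include infant anthropometrics and parent-report of infant appetite, infant diet, and parental feeding practices and beliefs". No other occasion is offered for appetite. The same section gives sessions to one arm only: "Participants assigned to the treatment condition will attend 3 intervention sessions at the Healthy Kids Lab". Protocol 1.d (Facilities) states the general rule that baseline and post-treatment outcome measures are collected at the SRC, and it places the sessions at the investigator's laboratory.

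The other two parent questionnaires given to both arms after treatment are tied to study visits alone. The food frequency questionnaire is the "Block Food Frequency Questionnaire for Children Aged 0-2 at the initial and post-treatment study visits". For the Infant Feeding Questionnaire (IFQ) the text reads "Parents will complete the IFQ, which assesses maternal feeding practices and beliefs, at the initial and post-treatment study visits".

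BEBQ subscales are compared between arms in Protocol section 4 and under the SAP's primary aim. Neither place says which visit's form is used, or how a form completed at a session is handled.

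**The concern.** A between-arm comparison needs the outcome to be collected in the same way in both arms. Here a treatment family may answer at the intervention laboratory, on the date of a session, while a control family can answer only at the SRC. A treatment family that misses the SRC visit also has a second route to a completed form, and a control family has none.

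The outcome matters because Aim 2 H2 rests on two BEBQ subscales, satiety responsiveness and food responsiveness. The programme content includes "parental attunement to infant satiety cues", so the setting where the form may be completed is also the setting where a closely related idea is taught. If collection differs with assignment, that difference becomes part of the observed group contrast.

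**Working it through.** The plan states no figure for this point, so there is nothing to reproduce. The check compares the places in the text and then works out what the fix would cost.

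**Comparison of the text**

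| Post-treatment item | Where it is to be completed | Open to both arms? |
|---|---|---|
| Appetite, Protocol 3.c.3(b) | SRC final study visit | Yes |
| BEBQ, Protocol 3.c.3(c) | SRC final study visit, or final treatment visit | Second option: treatment arm only |
| Food frequency questionnaire, 3.c.3(c) | Study visits | Yes |
| IFQ, 3.c.3(c) | Study visits | Yes |

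One of the three questionnaires given to both arms carries an alternative. Protocol 2.a.1 allocates 20 families to each arm, so at most 20 of 40 can use it.

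**Timing.** Session 3 and the final study visit each have a window of 9 months ± 30 days, and their order is not stated. For one treatment family the two occasions could be 0 to 30 + 30 = 60 days apart, in either order. The permitted age range is the same in both arms, so the difference lies in the place and date within that range.

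**Completeness.** Each treatment family that attends Session 3 but misses the SRC visit adds 1/20 = 5 percentage points to BEBQ completeness in its arm. The documents do not allow the number of such families to be estimated.

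**Precision if treatment forms are lost.** Assume equal standard deviations and 20 controls. The standard error of the difference is proportional to √(1/nT + 1/nC):

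- 20 v 20: √(1/20 + 1/20) = 0.3162
- 19 v 20: 0.3204, ratio 1.013 (+1.3%)
- 18 v 20: 0.3249 (+2.7%)
- 17 v 20: 0.3299 (+4.3%)
- 16 v 20: 0.3354 (+6.1%)
- 10 v 20: √(1/10 + 1/20) = 0.3873, ratio 1.22 (+22%)

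The numbers lost are illustrations with no source in the documents. The effect on the estimated group difference cannot be calculated, because no BEBQ standard deviation, uptake of the alternative or setting effect is given.

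**The case against.** The strongest reply is that this is loose wording. The Protocol generally calls the intervention contacts sessions, so a treatment visit is not a defined contact and could mean the post-treatment visit. The Facilities section already sends outcome collection to the SRC. This reading is possible and lowers confidence in the point. It does not settle the matter: the sentence sets the phrase beside the final study visit as an alternative, and nothing says that the two are the same.

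A second reply is that much of the suspected mechanism survives the fix. The SRC visit may fall on the same day as Session 3 or just after it, and the programme runs across the sessions at 4, 6 and 9 months. Parents are told their assignment at the first visit and know it wherever they answer. All of this stands. The fix removes the arm-dependent setting and completeness route, and nothing more.

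Third, few families may ever use the alternative: $50 is paid for the final study visit and no payment is listed for sessions. That is reasonable, but uptake is unknown.

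A reader might also infer that treatment families complete the form twice, or that a form completed at a session necessarily follows that day's teaching. The documents support neither. The wording describes one closing form with two possible places, and the order of form and content within a session is not given.

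**Conclusion.** The point holds as an inconsistency within the Protocol that, read literally, lets an outcome compared between arms be collected differently by arm. It affects one questionnaire and at most 20 of 40 families. It rests on taking the phrase at face value, and the loose-wording reading keeps confidence moderate. Severity is minor: this is a 40-family pilot and the correction is nearly free.

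A reader might go further and infer that the BEBQ comparison is biased, or biased in favour of the intervention. The documents do not support that. The size and direction of any bias are unknown, and it is not known whether any family used the alternative.

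**What to change.** In Protocol 3.c.3(c), delete the four words that offer the final treatment visit, so that both arms complete the BEBQ at the SRC final study visit. If a fallback for missed visits is wanted, offer the same one to both arms in the same window, and record the place and date of completion.

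The edit itself costs nothing. Without a common fallback, however, the post-treatment BEBQ is lost from any treatment family that attends Session 3 but misses the SRC visit. The number is unknown; at the illustrative 1 to 4 of 20, the standard error grows by 1.3% to 6.1%. Protocol section 4 would only consider a repeated measures likelihood model if data are missing, and the SAP omits it, so it should not be counted on to recover this loss.

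The SAP is written in the past tense, so data may already be collected. In that case, report the place and date of BEBQ completion by arm, which takes one table. A comparison limited to forms completed at the SRC is at most a sensitivity analysis. It could drop any number of treatment forms up to 20, including those of families who attended both contacts. Losing 10 would widen the standard error by 22%, and losing all 20 would leave no comparison. It also selects within one arm on something that happened after randomisation.

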#### **4. DATA ANALYSIS:**

Aim 1 (Determine the feasibility of the *HSF* intervention and family satisfaction with the treatment) will be explored using descriptive analyses. We will calculate the average number of treatment sessions attended and the percentage of participants attending 2 (67%) and 3 (100%) of the sessions. Additionally, we will calculate the percentage of caregivers who either "somewhat agree" or "strongly agree" that the intervention is appropriate, timely, helpful, and satisfactory as assessed by the Treatment Satisfaction Survey. Qualitative comments on the Treatment Satisfaction Survey will also be reviewed to identify themes regarding additional information to include in the intervention, what information was most helpful, what caregivers would like to see changed about the intervention, and what they would like to see stay the same.

Aim 2 (Examine the impact of the *HSF* intervention on growth trajectories, appetite regulation, and diet at post-treatment) will be explored through group comparisons between the control and treatment groups on weight-for-length scores, subscale scores of the *BEBQ*, and number of fruits and vegetables consumed in the last week as assessed on a food frequency questionnaire. Prior to between group comparisons, potential differences between the control and treatment group on key sociodemographic and baseline variables (e.g., gender, baseline weight-for-length, household income, caregiver education level) will be explored to confirm the

effectiveness of randomization to treatment condition. A series of Analysis of Variance (ANOVA) will be computed to examine whether the control and treatment groups differ on outcome variables. If missing data are present, we will also consider an alternative analyses using a repeated measures model with maximum likelihood estimation to examine group differences on outcome variables, which will allow inclusion of all participants despite missing data.

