College of Arts and Sciences
Department of Psychology
University of Cincinnati
Cincinnati, OH, 45221

Official Title: Healthy Start to Feeding Pilot Trial

Brief Title: Healthy Start to Feeding Intervention

NCT Number: NCT03597061

Document Date: 7/9/2018

Date Uploaded: 6/24/21

Document: Statistical Analysis Plan

Statistical Analysis Plan

Primary Aim (Examine the impact of the HSF intervention on growth trajectories, appetite regulation, and diet at post-treatment) was explored through group comparisons between the control and treatment groups on weight-for-length scores, subscale scores of the BEBQ, and number of fruits and vegetables consumed in the last week as assessed on a food frequency questionnaire. Prior to between group comparisons, potential differences between the control and treatment group on key sociodemographic and baseline variables (e.g., gender, baseline weight-for-length, household income, caregiver education level) were explored to confirm the effectiveness of randomization to treatment condition. A series of Analysis of Variance (ANOVA) were computed to examine whether the control and treatment groups differed on outcome variables.

Secondary Aim (Determine the feasibility of the HSF intervention and family satisfaction with the treatment) was explored using descriptive analyses. We calculated the average number of treatment sessions attended and the percentage of participants that attended 2 (67%) and 3 (100%) of the sessions. Additionally, we calculated the percentage of caregivers who either “somewhat agree” or “strongly agree” that the intervention was appropriate, timely, helpful, and satisfactory as assessed by the Treatment Satisfaction Survey. Qualitative comments on the Treatment Satisfaction Survey were also reviewed to identify themes regarding additional information to include in the intervention, what information was most helpful, what caregivers would like to see changed about the intervention, and what they would like to see stay the same.

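### The main Aim 2 analysis is a between-arm ANOVA with no stated role for the 3-month score; name ANCOVA on the infant's own 3-month value for weight-for-length and BEBQ

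*Protocol*

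**What the plan says.** Protocol section 4 (Data Analysis) states for Aim 2: "A series of Analysis of Variance (ANOVA) will be computed to examine whether the control and treatment groups differ on outcome variables". The SAP's Primary Aim paragraph has the same sentence in the past tense: "A series of Analysis of Variance (ANOVA) were computed to examine whether the control and treatment groups differed on outcome variables". Neither names a covariate, a change score or a time term. Both use baseline values explicitly only in a check that randomisation worked, and neither says what follows if it shows a difference.

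The protocol, but not the SAP, adds a second model: "If missing data are present, we will also consider an alternative analyses using a repeated measures model with maximum likelihood estimation". Its time points, terms and target contrast are not given.

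On measurement, the protocol's section on data collection tools says: "Anthropometrics will be measured for pre-post analyses at both the initial and final study visit by Bionutrition Core staff at the SRC". The BEBQ is completed "at both the initial study visit and final study visit or final treatment visit to assess current infant appetite". Allocation takes place "at their first study visit following completion of informed consent and baseline measures", so both 3-month scores precede randomisation. At the other end, "All participants will also complete a final study visit at the SRC at CCHMC when the child is 9 months". Between those visits only the intervention arm is measured: its "infants will also have length and weight measured at each treatment session to monitor safety of growth".

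The statement of Aim 2 (protocol section 1.a, repeated in section 4 and the SAP) refers both to growth trajectories and to the post-treatment time point.

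**The concern.** Two outcomes have a pre-randomisation measurement on the same scale, and the main analysis gives it no role. A 9-month comparison that ignores it may be less precise than it could be, which matters with 40 infants.

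The wording also leaves the estimated quantity partly open. The post-treatment wording points to 9-month scores. The pre-post label (attached to anthropometrics only) and the word trajectories point towards change. The two arms share only the 3- and 9-month measurements, so a trajectory compared between arms can be no more than a two-point change. The 9-month and change-score analyses differ in precision, and a reader of the results would need to know which one was run.

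**Working it through.** **Inputs from the documents.** 20 infants per arm (protocol section 2.a.1). Weight-for-length and BEBQ at 3 and 9 months. The sample size rests on feasibility, so there is no power figure to reproduce.

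**Assumptions, none of them in the documents.** Two-sided 0.05, 80% power, normal outcomes, equal SD at both visits, and a 3-to-9-month correlation r of 0.1, 0.2, 0.3, 0.5 or 0.7. As a sensitivity case, 16 per arm analysed (20% loss).

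**Formula.** Detectable difference in SD units = δ × √(v × 2/n). Here δ is the noncentrality giving 80% power for a t-test with the stated degrees of freedom, and v is the variance relative to a 9-month ANOVA.

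- 9-month ANOVA: v = 1, df = 2n − 2 = 38. δ = 2.875, so 2.875 × √(2/20) = 0.909 SD.
- ANCOVA: v = (1 − r²)(1 + 1/(2n − 4)) = (1 − r²)(1 + 1/36), df = 2n − 3 = 37. The second factor is the cost of estimating the slope.
- Change score: v = 2(1 − r), df = 38.

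| r | ANCOVA v | ANCOVA, SD | Change-score v | Change score, SD |
|---|---|---|---|---|
| 0.1 | 1.018 | 0.918 | 1.8 | 1.220 |
| 0.2 | 0.987 | 0.904 | 1.6 | 1.150 |
| 0.3 | 0.935 | 0.880 | 1.4 | 1.076 |
| 0.5 | 0.771 | 0.799 | 1.0 | 0.909 |
| 0.7 | 0.524 | 0.659 | 0.6 | 0.704 |

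ANCOVA beats the 9-month ANOVA only above r = 0.169. At r up to 0.3 the gain is at most 0.909 − 0.880 = 0.03 SD. The change score is less precise than ANCOVA at every r shown, and less precise than the 9-month ANOVA below r = 0.5. Power for a 0.5 SD difference is 34% with ANOVA and 33% to 57% with ANCOVA.

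With 16 per arm, the ANOVA detects 1.024 SD and ANCOVA 1.038, 1.022, 0.995, 0.903 and 0.745 SD. The break-even r is 0.192.

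**Chance imbalance.** The baseline difference between arms has SE √(2/20) = 0.316 SD, so it exceeds 0.3 SD in 34% of such trials and 0.5 SD in 11%. A 0.3 SD imbalance at r = 0.3 shifts the 9-month contrast by 0.3 × 0.3 = 0.09 SD. This shift is already inside the ANOVA standard error: 2/n = r² × 2/n (from baseline) + (1 − r²) × 2/n (the rest). It is the same loss as the precision loss above, seen within a single trial.

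**Open choice.** In simulated trials with no effect, at least one of the 9-month and change-score ANOVAs gives p < 0.05 in 8.5% to 9.3% of trials per outcome across these r. Either one fixed in advance gives about 5%.

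**The repeated-measures model.** Baselines are taken before randomisation and the arms share two visits. With complete baselines, a common baseline mean and one covariance matrix, the likelihood splits into the 3-month part and the 9-month score given the 3-month score and arm. Infants without a 9-month score contribute only to the first part. The arm estimate is therefore the ANCOVA coefficient in infants with 9-month data. A Wald z-test from plain ML rejects a true null about 7% of the time with 32 or 36 completers, instead of 5%.

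**The case against.** The strongest reply is that nothing here is wrong enough to need changing. The post-treatment wording recurs wherever Aim 2 is stated, and one ANOVA sentence covers all outcomes, including fruit and vegetable variety, which has no usable baseline. The natural reading is a 9-month comparison, and that test is unbiased over randomisations with 5% error. The benefit of ANCOVA depends on a correlation the documents do not give. For BEBQ, completed at entry when infants take only milk, it may be small enough that ANCOVA gains nothing. The trial is a pilot, and power for moderate effects stays low either way. The SAP is written as if the analyses were done.

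Most of this stands. It limits the point to precision and clarity, and rules out several stronger readings.

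- A reader might infer that the ANOVA is invalid or biased. It is not.
- A reader might count chance imbalance as a further harm. It is part of the same standard error.
- A reader might take 8.5% to 9.3% as the plan's error rate. It applies only if both ANOVAs are run and the better one is reported, and nothing in the documents says that will happen.
- A reader might say the protocol names nothing but an ANOVA. It also names the repeated-measures model, though only for consideration when data are missing.

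What the reply does not remove is that neither document gives the 3-month score a role in the main comparison, and that the pre-post label has no matching analysis.

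**Conclusion.** The point holds as a recommended improvement. The main Aim 2 analysis leaves out a pre-randomisation measurement of the same outcome, and the wording does not fully settle whether 9-month scores or changes are compared.

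Under the assumptions stated, moving from the 9-month ANOVA to ANCOVA changes the detectable effect from 0.91 SD to between 0.92 SD (r = 0.1) and 0.66 SD (r = 0.7). A change-score reading would do worse than ANCOVA throughout. The gain is negligible at low r and useful from about r = 0.5. It is more speculative for BEBQ than for weight-for-length. The trial was sized on feasibility, so this is no fatal flaw, but the SAP calls this comparison its Primary Aim and the change is nearly free.

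**What to change.** In both documents, state:

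> Continuous 9-month weight-for-length and each 9-month BEBQ subscale will be compared by ANCOVA, with arm as factor and the infant's own 3-month score on the same scale as covariate, whatever the balance check shows, reporting the adjusted difference and 95% CI.

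Then:

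- Bring the pre-post label and the growth-trajectory wording into line with this comparison.
- Do not add the plain ML model to the SAP, since it yields the same arm estimate as ANCOVA in infants with 9-month data. If a repeated-measures model is kept, fit it by REML with small-sample degrees of freedom, such as Kenward-Roger.
- Leave fruit and vegetable variety unadjusted, because eligibility excludes infants who have already had complementary foods.
- Treat the hypothesis on weight-for-length at or above the 85th percentile separately. It is binary, and this ANCOVA does not supply its analysis.
- If the analyses are already complete, report the ANCOVA beside the ANOVA, labelled as added.

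The cost is a sentence or two per document and one degree of freedom per model. No new data, visits or infants are needed. If r is near 0.1, the detectable effect worsens by about 0.01 SD (0.918 against 0.909 at 20 per arm; 1.038 against 1.024 at 16 per arm).
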